11.0 Safety Analysis

11.1 General Considerations

All safety analyses will be performed on the safety dataset. Treatment group differences in safety parameters are evaluated using two-sided test at the significance level of 0.050. When statistical tests are performed, the comparisons will be between each ABBV-8E12 dose and placebo. With the exception of adverse events, all safety assessments that are taken no more than 45 days after the last dose of study drug will be included in the safety evaluation of the Double-blind Treatment Period. All safety assessments that are taken more than 45 days but no more than 20 weeks after the last dose of study drug will be included in the safety evaluation for the Post-Treatment Follow-Up Period.

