8.1.6 Safety Analyses

All safety analyses will be performed on the safety data set unless otherwise specified. Comparisons between each ABBV-8E12 dose group and placebo will be performed with two-sided test at the significance level of 0.050, if applicable. All safety assessments that are taken no more than 20 weeks after the last dose of study drug administration will be included in the safety evaluation of the Double-blind Treatment Period, and all safety assessments that are taken more than 20 weeks after the last dose of study drug will be included in the safety evaluation for the Post-treatment Follow-up Period.

Study Drug Exposure and Compliance

The number of doses on study drug will be summarized by treatment group and all treatment groups combined. The number and percentage of subjects with at least 90% compliance with study drug dosing will be summarized by treatment group and all treatment groups combined.

Adverse Events

A treatment-emergent adverse event (TEAE) is defined as any adverse event that begins or worsens in severity on or after the first study drug dose date and no more than 20 weeks after the last study drug dose date.

All other safety assessments that are taken no more than 20 weeks after the last dose of study drug will be included in the safety evaluation of the Double-blind Treatment Period, and all safety assessments that are taken more than 20 weeks after the last dose of study drug will be included in the safety evaluation for the Post-treatment Follow-up Period.

Unless otherwise specified, treatment group differences in continuous safety variables (e.g., change from baseline to final observation on laboratory tests) will be assessed using an ANOVA model with treatment as the main effect, and the treatment group differences in binary safety variables will be evaluated using Fisher's exact test.

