8.1.6.1 Analysis of Adverse Events

Adverse events will be coded using the most current version of the Medical Dictionary for Regulatory Activities (MedDRA). The number and percentage of subjects who report TEAEs will be tabulated by MedDRA system organ class (SOC) and preferred term for each treatment group, overall ABBV-8E12 and all treatment groups combined. Treatment group differences between each ABBV-8E12 dose group and the placebo group will be analyzed using Fisher's exact test.

The number and percent of subjects experiencing treatment-emergent SAEs (including deaths) and adverse events leading to premature discontinuation of study drug will be tabulated by MedDRA SOC and preferred term for each treatment group, overall ABBV-8E12 dose groups, and all treatment groups combined. Treatment group differences between each ABBV-8E12 dose groups and placebo will be analyzed using Fisher's exact test.

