4.0 Study Objectives, Design and Procedures

4.1 Objectives

The primary objectives of this study are:

- To assess the efficacy of ABBV-8E12 in slowing disease progression in subjects with progressive supranuclear palsy as measured by the PSP Rating Scale (PSPRS).
- To assess the long term safety and tolerability of ABBV-8E12 for up to 52 weeks in subjects with progressive supranuclear palsy.

The secondary objectives of this study are:

- To assess the pharmacokinetics of multiple doses of ABBV-8E12 in subjects with progressive supranuclear palsy.

- To assess the efficacy of ABBV-8E12 in slowing disease progression and functional impairment in subjects with progressive supranuclear palsy as measured by secondary endpoints.
- To assess the efficacy of ABBV-8E12 in slowing regional and/or whole brain atrophy in subjects with progressive supranuclear palsy as measured by volumetric magnetic resonance imaging (MRI).

The exploratory objectives of this study are:

- To assess the efficacy of ABBV-8E12 in slowing disease progression and functional impairment in subjects with progressive supranuclear palsy as measured by exploratory endpoints.
- To assess the effect of ABBV-8E12 on cerebrospinal fluid (CSF) free/total tau protein levels.
- To assess the effect of ABBV-8E12 on potential CSF biomarkers of disease progression.

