11.2.1 Adverse Event Overview

The number and percentage of subjects experiencing one or more adverse events in the following adverse event categories will be summarized for each treatment group, ABBV-8E12 Overall. No comparisons of treatment groups will be performed.

- Any TEAE
- Any TEAE that was rated as having reasonable possibility of being related to study drug by the investigator
- Any severe TEAE
- Any serious TEAE
- Any TEAE that led to discontinuation of study drug
- Any fatal TEAE
- All deaths

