11.2.2 Adverse Event Incidence

TEAE incidence will be summarized and presented using primary MedDRA system organ classes (SOCs) and preferred terms (PTs). The system organ classes will be presented in alphabetical order and the preferred terms will be presented in alphabetical order within each system organ class. Subjects reporting more than one adverse event for a given MedDRA PT will be counted only once for that term. Subjects reporting more than one adverse event within a SOC will be counted only once for the SOC total. Subjects reporting more than one adverse event will be counted only once in the overall adverse event total.

The number and percentage of subjects experiencing one or more TEAEs will be summarized by PT for each treatment group, ABBV-8E12 Overall. The PTs will be presented by decreasing frequency in ABBV-8E12 Overall.

The number and percentage of subjects experiencing one or more adverse events in the following adverse event categories will be summarized by primary SOC and PT for each treatment group, ABBV-8E12 Overall.

- Any TEAE
- Any serious TEAE
- Any TEAE that led to discontinuation of study drug

- Any TEAE assessed by the investigator to have Reasonable Possibility of Being Related to study drug

The number of subjects experiencing one or more TEAEs will also be summarized by maximum severity category (mild, moderate, severe and unknown) and primary SOC and PT for each treatment group, ABBV-8E12 Overall. Subjects reporting more than one TEAE for a given PT will be counted only once for that term in the most severe category reported. If a subject has an adverse event with unknown severity, then the subject will be counted in the severity category of "unknown" even if the subject has another occurrence of the same event with a severity present. The only exception is if the subject has another occurrence of the same adverse event with the most extreme severity – "Severe." In this case, the subject will be counted under the "Severe" category. No comparisons of treatment groups will be performed.

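### Protocol and SAP do not agree on how adverse events are compared with placebo, and neither gives an interval for any adverse-event difference, although safety is a primary objective

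*SAP*

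**What the plan says.** - **Objective.** SAP 4.1, like Protocol 4.0, lists as its second primary objective: "To assess the long term safety and tolerability of ABBV-8E12 for up to 52 weeks in subjects with progressive supranuclear palsy".
- **Protocol, general rule (8.1.6).** "Comparisons between each ABBV-8E12 dose group and placebo will be performed with two-sided test at the significance level of 0.050, if applicable". Binary safety variables are assigned to Fisher's exact test unless otherwise specified.
- **Protocol, adverse events (8.1.6.1).** For TEAEs by system organ class (SOC) and preferred term (PT): "Treatment group differences between each ABBV-8E12 dose group and the placebo group will be analyzed using Fisher's exact test". The same rule is repeated for serious events, including deaths, and for events leading to discontinuation of study drug. No risk difference, ratio or interval is named.
- **SAP, general rule (11.1).** "Treatment group differences in safety parameters are evaluated using two-sided test at the significance level of 0.050", followed by a qualifier: "When statistical tests are performed, the comparisons will be between each ABBV-8E12 dose and placebo".
- **SAP, overview (11.2.1).** For any, related, severe, serious, discontinuation-causing and fatal TEAEs and for all deaths: "No comparisons of treatment groups will be performed". The tables by maximum severity and by maximum relationship in 11.2.2 also exclude comparisons.
- **SAP, incidence tables (11.2.2).** "The number and percentage of subjects experiencing one or more TEAEs will be summarized by PT for each treatment group, ABBV-8E12 Overall". The SOC/PT tables for any, serious, discontinuation-causing and related TEAEs are described in the same way. They neither name a test nor exclude one.
- **SAP, other safety data.** Sections 11.3.1, 11.4.1, 11.5.1 and 11.6.2 give p-values with 95% confidence intervals for mean changes. Section 11.6.3 says MRI safety findings will be compared between each dose and placebo, without naming a method. Section 8.0 tests discontinuation reasons by Fisher's exact test.
- **SAP, record of changes (14.0).** Nothing is listed about the adverse-event comparison.

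**The concern.** A programmer cannot tell from the two documents whether serious TEAEs are to be tested. The protocol says yes. The SAP's general rule says yes where tests are performed, its overview says no, and its SOC/PT tables are silent. SAP 11.2.2 counts each subject once in an overall adverse-event total, so the same headline count can appear in the overview, where comparison is ruled out, and in an SOC/PT table, where it is left open.

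Whichever route is followed, the report lacks the quantity that a safety objective needs: the size of the excess risk and how large an excess the data still allow. A Fisher p-value alone does not supply it, and neither do bare percentages. The gap matters most for infrequent serious events and deaths, where 110 subjects per arm carry little information and a non-significant result is easily over-read.

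**Working it through.** **1. Inputs.** 110 subjects per arm, 1:1:1 (Protocol 8.2, SAP 4.3). The safety set is everyone dosed (SAP 5.1), so I take 110 v 110. The level is two-sided 0.050, each dose against placebo, with no multiplicity adjustment. The documents give no expected adverse-event rates, so those below are assumptions.

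**2. The plan's own power figure.** The only one for the treatment comparisons concerns the PSPRS. With 25% missing there are 110 × 0.75 = 82.5 evaluable subjects per arm. At two-sided 0.025, power for an effect size of 0.56 is Φ(0.56 × √(82.5/2) − 2.241) = Φ(1.355) = 91.2%, which agrees with the SAP's approximate 90%. For 0.28 it is Φ(−0.443) = 32.9%. No power or precision is stated for safety.

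**3. Power of Fisher's test to detect a doubling.** Power = Σ over x₀, x₁ of Bin(x₀; 110, p₀) × Bin(x₁; 110, p₁) × I[Fisher p ≤ 0.05], by enumerating every 2×2 table:

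| Placebo v active rate (assumed) | Power |
|---|---|
| 2% v 4% | 5.3% |
| 5% v 10% | 21.4% |
| 8% v 16% | 37.6% |
| 10% v 20% | 48.0% |
| 15% v 30% | 71.7% |
| 20% v 40% | 87.9% |

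Power for a doubling passes 50% at a placebo rate of about 10.4% and 80% at about 17.3%. Part of the loss comes from the conservatism of the exact test: its actual type I error is 2.3% at a common rate of 5% and 3.0% at 10%.

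**4. What an interval would add.** The Newcombe limits for d = p₁ − p₀, with Wilson limits (l, u) for each arm, are:
- lower = d − √[(p₁ − l₁)² + (u₀ − p₀)²]
- upper = d + √[(u₁ − p₁)² + (p₀ − l₀)²]

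For 10/110 v 5/110, the Wilson limits are 0.0501 to 0.1593 and 0.0196 to 0.1020, and d = 0.0455:
- lower = 0.0455 − √(0.0408² + 0.0565²) = −0.024
- upper = 0.0455 + √(0.0684² + 0.0259²) = 0.119

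| Active v placebo events (of 110 each) | Fisher p | Risk difference, points (95% CI) |
|---|---|---|
| 10 v 5 | 0.28 | 4.5 (−2.4 to 11.9) |
| 11 v 5 | 0.19 | 5.5 (−1.7 to 12.9) |
| 22 v 11 | 0.058 | 10.0 (0.5 to 19.5) |
| 44 v 22 | 0.002 | 20.0 (7.9 to 31.3) |

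In the first two rows the p-value is unremarkable, while an excess of more than 11 points remains compatible with the data. In the third row the test just misses 0.05 although the interval lies above zero. The two methods can disagree at the boundary because Fisher's test is conservative and the Newcombe interval is not its inversion.

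**The case against.** The strongest reply is that the documents can be read as compatible. The protocol attaches Fisher's test to SOC/PT tabulations. The SAP's SOC/PT tables do not exclude a test, SAP 11.1 supplies the 0.050 rule, and the SAP's exclusions cover only the overview, severity and relationship tables. That reading is possible, so a reader who infers that the SAP drops adverse-event comparisons altogether goes too far. Discontinuation reasons are Fisher-tested and MRI findings are to be compared. For the same reason, the silence of SAP 14.0 is not proof of an unrecorded departure. But the reading has to be assembled by inference, and it still leaves no interval.

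A reader might also infer that the plan treats p above 0.05 as showing no difference. Neither document says so, and both qualify when safety tests apply. Over-reading is a risk that the wording leaves open, not a rule in the plan. Nor is a doubled rate usually missed in general: at placebo rates of 15% to 20%, power is 72% to 88%.

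Finally, safety is a primary objective without a tested hypothesis. The data monitoring committee reviews unblinded safety data repeatedly, and listings of serious events and deaths are planned. Published counts would let anyone compute the interval. All of this stands. It makes the point one of analysis and reporting, not a gap in the monitoring of subjects. It does not explain why laboratory means get 95% intervals and serious events get none.

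**Conclusion.** The concern holds in limited form. Protocol 8.1.6.1 and SAP 11.1, 11.2.1 and 11.2.2 do not give one clear instruction on whether and how adverse events are compared, and neither document plans an interval for any adverse-event contrast. At 110 per arm, Fisher's test has 21% power for 5% v 10% and 48% for 10% v 20%, so a non-significant result is weak evidence for events with a placebo rate of about 10% or less. It is considerably more informative for common events.

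These figures assume that all 110 per arm are dosed, that events are counted by subject, and that the event rates are as shown. The conflict between the documents and the missing intervals depend on none of these assumptions.

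**What to change.** 1. In SAP 11.2.1, and for MRI findings in 11.6.3, report the risk difference (each dose minus placebo) with a 95% confidence interval, by Miettinen-Nurminen or Newcombe. Cover any TEAE, severe TEAE, serious TEAE, TEAE leading to discontinuation, death, and new or worsening MRI findings.
2. State that a p-value above 0.05 is not evidence of no difference.
3. Reconcile SAP 11.1, 11.2.1 and 11.2.2 with Protocol 8.1.6.1 on whether and how adverse events are compared, and record the change in SAP 14.0.

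No new data are needed. The cost is a few more table columns, plus either a protocol wording change or a recorded departure from it. The intervals would be unadjusted: six categories by two doses gives 12, of which 12 × 0.05 = 0.6 would be expected to miss the true difference at nominal coverage, and more if several MRI findings are listed separately. They should be labelled descriptive.

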No subject experienced a systemic hypersensitivity reaction or injection site reaction, and there have been no clinically relevant patterns of adverse events (AEs) or abnormal laboratory findings observed. Based on available anti-drug antibody (ADA) data in Study C₂N-8E12-WW-104, no ADAs have been detected in post-dose samples on Day 14 and Day 28.

The plasma pharmacokinetic data from Study C₂N-8E12-WW-104 indicate dose-proportional increases in area under the concentration time curve (AUC) from 2.5 to 50 mg/kg. The mean time to maximum plasma concentration (T_{max}) ranged from 0.3 hours to 4.6 hours, and half-life ranged from 27 to 37 days.

Cerebrospinal fluid (CSF) concentrations increased with dose, and the CSF/plasma ABBV-8E12 ratio ranged from 0.181% to 0.385%.

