8.1.6.2 Analysis of Laboratory Tests

Change from baseline to each double-blind visit value and to the minimum, maximum and final double-blind value will be presented for each continuous hematology, chemistry and urinalysis parameters. Treatment differences between each ABBV-8E12 dose group and placebo in change from baseline to minimum, maximum and final clinical laboratory evaluation will be analyzed using one-way ANOVA with treatment as the main effect.

For each treatment group, shift tables will be generated showing the number and percentage of subjects with low, normal, high and missing values at baseline and final observation based on the reference ranges provided by each laboratory.

The number and percentage of subjects in each treatment group who have values meeting predefined criteria for potentially clinically significant values ([Appendix D](#)) at any time after the first dose of study drug and no more than 20 weeks after the last dose of study drug will be summarized separately for hematology and chemistry variables.

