8.1.6.3 Analysis of Vital Signs and Weight

Vital sign variables include pulse rate, systolic blood pressure, and diastolic blood pressure, body temperature, weight, and BMI. Pulse rate and blood pressure variables will include measurement in the supine position, measurement in the standing position and the orthostatic change (from supine to standing).

Change from baseline to each double-blind visit value and to the minimum, maximum and final double-blind value will be presented for each vital sign and weight variable and analyzed using one-way ANOVA with treatment as the main effect.

The number and percentage of subjects in each treatment group who have values meeting predefined criteria for potentially clinically significant values (definitions will be provided in the Statistical Analysis Plan) at any time after the first dose of study drug and no more than 20 weeks after the last dose of study drug will be summarized.

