8.1.6.4 Analysis of ECG Variables

ECG variables include heart rate, PR, QRS, QT, and QTcF intervals. Change from baseline to final double-blind value will be presented for each ECG parameter and analyzed using one-way ANOVA with treatment as the main effect.

The number and percentage of subjects in each treatment group who have values meeting predefined criteria for potentially clinically significant values at any time after the first dose of study drug will be summarized.

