11.3.3 Potentially Clinically Significant Laboratory Values

Criteria for potentially clinically significant (PCS) values have been predefined for selected laboratory variables as outlined in [Appendix A](#). For each variable, a summary of

the number and percentage of subjects in each treatment group who have at least one double-blind observation that meets the PCS criteria and is more extreme than their baseline value will be provided. A listing will also be prepared that will include, for each variable, all observations for each subject that met the PCS criteria for that variable at any time during the study. PCS analysis for laboratory values will also be prepared by geographical region. No comparisons of treatment groups will be performed.

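### The SAP's counts of potentially clinically significant (PCS) values stop 45 days after the last dose, the protocol's run to 20 weeks, and the SAP does not record the change

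*SAP*

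**What the plan says.** **Protocol.** Section 8.1.6 sets the general rule for the double-blind safety evaluation: "All safety assessments that are taken no more than 20 weeks after the last dose of study drug administration will be included". The PCS sections then give their own windows:

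- Laboratory (8.1.6.2): PCS values are counted "at any time after the first dose of study drug and no more than 20 weeks after the last dose of study drug".
- Vital signs and weight (8.1.6.3): values "no more than 20 weeks after the last dose of study drug will be summarized".
- ECG (8.1.6.4): values "at any time after the first dose of study drug will be summarized". This sentence has no upper limit, so only the general 20-week rule bounds it.

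**SAP.** Section 11.1 exempts adverse events and then ends the double-blind evaluation of everything else at 45 days: "all safety assessments that are taken no more than 45 days after the last dose of study drug will be included". Values from day 46 to week 20 go to a separate post-treatment follow-up evaluation. Section 11.3.3 counts subjects with "at least one double-blind observation that meets the PCS criteria" and a value more extreme than at baseline. Sections 11.4.2 and 11.5.2 apply the same rule to vital signs, weight and ECG. No PCS count is planned for the follow-up period. Treatment-emergent adverse events keep 20 weeks (SAP 11.2).

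SAP Section 14 lists changes from the protocol, such as the interim multiplicity method, the sample size, the addition of Japan and the regional analyses. The safety window is not among them.

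**The concern.** Long-term safety and tolerability is a primary objective. The PCS table is where a reader sees, by arm, what proportion of subjects reached an extreme value. Under the SAP, a subject whose only such vital sign or ECG occurs at a follow-up visit is not counted there, although the protocol says that the subject should be.

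The windows also disagree within the SAP. A late event can count as treatment-emergent while the vital sign or ECG behind it falls outside its PCS table. A late laboratory value can count in the whole-study shift table but not in the PCS table. Protocol 6.1.4 gives the reason for collecting adverse events for 20 weeks, namely that this is about five half-lives. The SAP gives no reason for a shorter period for measured values.

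**Working it through.** **Inputs**

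- Half-life: "half-life ranged from 27 to 37 days" (Protocol 3.0, from the single-dose study).
- Protocol window: 20 weeks = 20 × 7 = 140 days. SAP window: 45 days.
- Last scheduled dose: Dose 14 at Week 48, Day 337 (Protocol 5.1 and Appendix C).
- Scheduled late measurements (SAP 6.2): vital signs and C-SSRS at Weeks 60 and 68, ECG at Week 60. The C-SSRS has no PCS table and is summarised over the whole study (SAP 11.6.1).

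**Check of the plan's own figure.** Protocol 6.1.4 equates 20 weeks with about five half-lives. 140/27 = 5.2, 140/28 = 5.0 and 140/37 = 3.8. The figure reproduces at the short end of the half-life range.

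**Visit timing.** Week w falls on Day 7w + 1, so days since Dose 14 = 7w + 1 − 337.

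- Week 52: 365 − 337 = 28 days, inside both windows.
- Week 60: 421 − 337 = 84 days, outside the SAP window and inside the protocol's.
- Week 68: 477 − 337 = 140 days, outside the SAP window and exactly at the protocol's limit.

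**Drug remaining.** Fraction = 0.5^(days / half-life), assuming mono-exponential decline.

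| Days after last dose | Half-life 27 days | Half-life 37 days |
|---|---|---|
| 45 (SAP cut) | 0.5^(45/27) = 31.5% | 0.5^(45/37) = 43.0% |
| 84 (Week 60) | 0.5^(84/27) = 11.6% | 0.5^(84/37) = 20.7% |
| 140 (Week 68) | 0.5^(140/27) = 2.8% | 0.5^(140/37) = 7.3% |

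**Share of the post-dose window leaving the counts.** (140 − 45)/140 = 95/140 = 68%.

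**Laboratory values.** SAP 6.2 schedules laboratory tests only to Week 52 and defines no post-treatment laboratory window. The activity tables, as far as they can be read, agree. A laboratory value can therefore leave the PCS count only through a late discontinuation visit or an unscheduled test. For example, doses are 28 days apart, so a subject who misses one dose and has the discontinuation visit at the following dosing date is 2 × 28 = 56 days past the last dose.

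**Where later values still appear.** They are in the PCS listings, which cover the whole study (SAP 11.3.3, 11.4.2, 11.5.2). Laboratory shift tables by arm also cover the whole study (11.3.2). Post-treatment mean changes are planned for laboratory, vital signs and ECG (11.3.1, 11.4.1, 11.5.1).

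**The case against.** The best defence is that the SAP reorganises the data and loses little. The protocol's own split is awkward: it places everything up to 20 weeks in the double-blind period and reserves the follow-up evaluation for data beyond 20 weeks, although follow-up itself lasts only about 20 weeks. The SAP's split makes that follow-up category usable. Separate windows for adverse events and measured values are not an error in themselves. A PCS laboratory value must also be reported as an adverse event or have the reason for not doing so documented (Protocol 5.3.1.1), so a late one has a second route into incidence by arm. Subjects who enter the extension have no follow-up visits in this study.

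All of that stands, and it limits the point. It also rules out three stronger readings that a reader might infer:

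- *That the SAP discards safety data after 45 days.* It does not. SAP 11.1 moves those data to a follow-up evaluation, and adverse events are exempt.
- *That a third to two fifths of the antibody is still present at the lost visits.* That range belongs to day 45, when no follow-up visit is scheduled. At the first excluded visit it is about 12% to 21%.
- *That late laboratory abnormalities go uncounted.* The shift tables count them by arm against reference ranges, though not against PCS thresholds, and few should arise.

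What the defence does not answer is the PCS tables themselves. A listing gives no percentage by arm, and a mean change does not show how many subjects had an extreme value. The SAP offers no reason for the shorter window and does not list it as a change.

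**Conclusion.** The conflict is real and narrow. For laboratory and vital-sign PCS counts the two documents state different windows outright. For ECG the protocol sentence has no end, and the general rule supplies 20 weeks. Followed as written, the SAP leaves the Week 60 vital signs and ECG and the Week 68 vital signs out of the PCS percentages by arm that the protocol specifies, for subjects who do not enter the extension. Laboratory counts are affected only at the margin.

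The documents do not say how many subjects will enter follow-up, so the number affected cannot be given. The drug fractions assume mono-exponential decline at a half-life from single doses and are approximate. The conflict itself does not depend on them. This should be corrected before the tables are run, but it does not threaten the efficacy analysis or the adverse-event tables.

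**What to change.** In SAP 11.3.3, 11.4.2 and 11.5.2, count subjects with a PCS value at any post-baseline observation through 20 weeks after the last dose. Keep the 45-day count as an on-treatment supplement. An acceptable alternative is a PCS table for day 46 to week 20 plus a combined count.

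State the end of the window so that Week 68 is not lost. It falls exactly on day 140, and Appendix C allows visits ± 4 days, so with Dose 14 on its nominal day a permitted visit can fall as late as 140 + 4 = 144 days. A strict 140-day limit would drop it.

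Record any remaining departure from Protocol 8.1.6 in SAP Section 14, with the reason. If the sponsor prefers the 45-day split for the other safety summaries, the same entry can explain it.

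The cost is SAP wording and a re-run of planned tables on data already being collected. No new visits, data or subjects are needed.
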